Sample size determination. We will enroll 66 participants and expect 50 to complete the study. This drop-out rate accounts for participant non-compliance. In our previous Sleep Study, our completion rate was 90%. We expect a larger drop-out rate in the proposed study due to the longer duration of each treatment phase, and we also anticipate dismissing some participants due to non-compliance. Each participant will undergo 2 study phases, and each response variable will be measured at least once per phase. Thus, for each response measure we will have at least  $50 \times 2$  paired observations. We have analyzed preliminary data consisting of a number of measurements from 2 overweight women from our Pilot Study. Based on preliminary data analysis we have estimated an effect size (mean paired difference) of  $0.69 \pm 0.36$  g for fat mass and an effect size (mean paired difference) of  $0.91 \pm 0.65$  g for weight gain. This translates to very large effect sizes of 1.92 (fat mass) and 1.4 (weight gain) for paired t-tests. With these effect sizes we have more than 99% power for paired t-tests.] We have estimated the EI effect size to be  $295.9 \pm 116.3$  kcal [8]. The effect size for a paired t-test (effect size divided by the standard deviation) for a paired t-test is >2, which is a very large effect size for paired t-test. This means with  $50 \times 2$  paired samples, we have >80% power for paired t-test. In [name] et al. 2011 [8], we also reported an effect size of  $20.7 \pm 6.8$  g for fat intake and an effect size of  $57.9 \pm 32.6$  g for carbohydrate intake. This translates to very large effect sizes of 3.04 and 1.78, respectively for fat and carbohydrates for paired t-test. With these effect sizes we have >80% power for paired t-test. Moreover, using the R^2 value from our linear model analysis of [name] et al. 2011, we determined that we have >80% power for proposed linear mixed model analyses (as described in statistical plan) with energy balance, fat and carbohydrate intakes. Thus, we have very good power overall, which will be useful in our primary analyses as well as in exploring sex differences. Statistical plan. Exploratory data analyses for physiological, anatomical, biomarker and intakerelated responses will be performed using R, SAS and other software. As part of the analysis, we will compute descriptive statistics for each variable. In particular, we will compute the proportion, mean, variance, standard error and the range of continuous variables and frequency and mode for discrete variables. Descriptive statistics will be computed for each specific sleep phase. In addition, correlation coefficients between the variables will be computed and scatter plots will be checked for linear relationships. The correlations and scatter plots help assess the degree of collinearity among variables, which will be useful for interpreting regression-based linear mixed model analyses discussed later. The data will be tested for normality, and if needed an appropriate transformation will be used on the raw data to make the normal approximation better. We will have a comprehensive strategy to deal with missing data. We will study missingness to decide if the data are missing at random or missing completely at random. Missing rates will also be estimated for each variable. Missing values will be imputed, as appropriate. We will fit a linear mixed model to analyze the data. Treatments (sleep duration: SR vs. HS) will be fixed effects and subjects a random effect. As we are collecting data from two phases for each subject, we will test for carryover effects by using a treatment x phase interaction in an initial version of each linear model. If the interaction term is not significant then we will rebuild the linear model without the interaction term. The other independent variables (covariates) will be sex, age, baseline BMI, and race/ethnicity. If required anywhere in the analysis plan, p-values will be adjusted for multiple comparisons. Sp. Aim 1: Hypothesis 1a. SR will lead to increased total adipose tissue mass, as assessed using MRI, relative to HS. We will perform repeated measure linear mixed model analyses separately for adipose tissue mass increase and weight gain (as the response). Sleep duration (SR vs. HS) and the covariates will be used as independent variables. Subject will be used as a random effect. Paired t-test and Wilcoxon test will be used to determine whether the SR and HS have different

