
NIH Toolbox measures (from HS to SR), to test if these values are significantly different between older and young participants. Aim 5: (To determine whether the effects of SR on cognitive outcomes are moderated by brain atrophy in younger and older adults. Hypothesis 5a. The effect of mild SR on cognition will be greater among individuals with greater amounts of cortical thinning, smaller hippocampi, and greater WMH volume. This effect will be greater in older relative to younger adults.) Separately for older and young participants, we will perform linear model analyses, with average differences in NIH Toolbox measures (from HS to SR) as outcomes (separately for each outcome). Cortical length, hippocampi size and WMH volume will be used as independent variables. We will apply covariates as independent variables, if they are found to be significant in an initial analysis. Then, we will pool the datasets to include both older and young participants. In the pooled data, we will perform linear model analyses, with average differences in NIH Toolbox measures (from HS to SR) as outcomes. Cortical length, hippocampi size, WMH volume and age group (older vs. younger) will be used as independent variables. We will also use covariates as independent variables, if they are found to be significant in an initial analysis. Aim 6: (To determine whether changes in metabolic or hormonal profiles mediate changes in cognitive function as a result of SR. Hypothesis 6a. The effect of mild SR on cognition will be mediated by changes in hormones (leptin, adiponectin, and insulin).) Separately for older and young participants, and separately for each hormone measure, each outcome (from NIH toolbox) will be analyzed with mediation analysis (Baron and Kenny's method). Sleep type (SR. vs HS) will be the predictor in the analysis. Hormone measure will be used as the potential mediator. As we have multiple measures from each participant, each component analysis in Baron and Kenny's method will be done as linear mixed model analysis, with subject as random effect. Within each mediation analysis, the first analysis will only have one fixed effect: sleep (SR vs. HS). The outcome measure will be the dependent variable. If sleep is found to be significant, then the second analysis will be done with the hormone measure as the dependent variable, and sleep as the fixed effect. If sleep is also found to be significant in the second analysis, then in the final analysis, the outcome measure will be the dependent variable. Fixed effects will be sleep and the hormone measure. If the hormone measure is still found to be significant, and the coefficient of sleep has decreased in absolute value from the first analysis, then a mediation effect of hormone will be concluded.

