Structural brain imaging MRI protocol. MRI scanning will take place on a 3T Philips Achieva scanner located at Columbia University Irving Medical Center. This procedure will take place in conjunction with the whole-body scan that is currently performed in the parent study and will only be performed at baseline of phase 1. The protocol derives measures of brain atrophy/volumetry and WMH, but we will also examine microbleeds and infarcts for secondary analyses. Table 1 displays the pulse sequences collected for this study. Scanning takes place in a single session and includes a high-resolution T1-weighted anatomical scan (MPRAGE), T2-weighted FLAIR, and gradient echo (GRE). We also collect diffusion-weighted imaging and diffusion tensor imaging data for secondary or exploratory analyses. The MRI data will be transferred to a PACS for clinical review and via established, secure DICOM servers the data are also transferred to [name] laboratory for analysis.

Global and regional atrophy. Using each individual's T1-weighted image, structural imaging measures of both global and regional brain volume and measures of cortical thickness are derived with FreeSurfer (<http://surfer.nmr.mgh.harvard.edu/>). Primary volumetric measures will be hippocampal, entorhinal cortex, and total brain volume. We will also assess cortical thickness as specific patterns of cortical thinning found in Alzheimer's disease [20, 46]. Again using Freesurfer software [47, 48], we will calculate mean thickness in 33 different gyral-based areas in each hemisphere [49]. The primary cortical thickness measure [20, 46] will include the average thickness in Alzheimer's disease -related regions [50]. Volumetric and cortical thickness in all regions are databased for secondary analyses.

Microbleeds. Microbleeds are rated by visual inspection following criteria put forth by Greenberg et al. [51-53]. The primary measure is the presence or absence of lobar microbleeds, indicating possible or probable cerebral amyloid angiopathy [54]. The number of microbleeds and location are coded and databased for each participant.

Infarct. All available MRI data are used to define radiological infarcts. Infarcts are rated as discrete hypointense lesions that are larger than 5mm surrounded by a complete hyperintense ring on FLAIR. The primary measure is presence or absence of infarct, but several summary measures are generated, including number, size, and location.

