activity in networks associated with reward and food valuation (insula, orbitofrontal cortex) during a period of SR relative to HS. These responses will be correlated with intakes of high carbohydrate and high fat foods (hypothesis 1a) and ghrelin. Connectivity of the networks involved in reward valuation at rest will be stronger after SR compared to HS and synchrony of the DMN will be reduced after SR compared to HS. **Aim 3:** Does Longer, milder SR, as observed in individuals with SSD adverse cardiometabolic risk profile? **Hypothesis 3a:** SR will lead to increased glucose, insulin, triglycerides, and reduced high density lipoprotein cholesterol and adiponectin relative to HS. **Hypothesis 3b:** Increased adiposity and poor diet quality (higher fat and carbohydrates) after SR will partially explain the adverse cardio-metabolic risk profile associated with SR. **Aim 4.** To determine whether long-term mild SR, relative to HS, challenges acute cognitive outcomes in older and younger adults. **Hypothesis 4a.** Mild SR will induce cognitive decline, assessed with the NIH Toolbox, which will be greater in older relative to younger adults. **Aim 5.** To determine whether the effects of SR on cognitive outcomes are moderated by brain atrophy and small vessel cerebrovascular disease in younger and older adults. **Hypothesis 5a.** The effect of mild SR on cognition will be greater among individuals with greater amounts of cortical thinning, smaller hippocampi, and greater WMH volume. This effect will be larger in older relative to younger adults. **Aim 6.** To determine whether changes in metabolic or hormonal profiles mediate changes in cognitive function as a result of SR. **Hypothesis 6a.** The effect of mild SR on cognition will be mediated by changes in hormones (leptin, adiponectin, and insulin).

---

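### The pooled Aim 5 model has no age-group by brain-measure terms, so it does not test whether moderation is stronger in older adults

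*Combined protocol and SAP*

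**What the plan says.** Under Statistical Procedures, Aim 5, Hypothesis 5a has two parts. The first is moderation: "The effect of mild SR on cognition will be greater among individuals with greater amounts of cortical thinning, smaller hippocampi, and greater WMH volume". The second follows at once: "This effect will be greater in older relative to younger adults". Research Question(s)/Hypothesis(es) repeats both, the second as "This effect will be larger in older relative to younger adults".

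The analysis has two steps.

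- Stratified step: "Separately for older and young participants, we will perform linear model analyses, with average differences in NIH Toolbox measures (from HS to SR) as outcomes". The three brain measures are the predictors.
- Pooled step, on the same outcome: "Cortical length, hippocampi size, WMH volume and age group (older vs. younger) will be used as independent variables". The only other terms come from this sentence: "We will also use covariates as independent variables, if they are found to be significant in an initial analysis".

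No product of age group and a brain measure is named in either step, and no comparison of the stratified slopes is described. The one product term in the statistical plan concerns carryover: "we will test for carryover effects by using a treatment x phase interaction in an initial version of each linear model".

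Both steps name cortical *length*. The structural brain imaging section under Procedures derives thickness: "The primary cortical thickness measure [20, 46] will include the average thickness in Alzheimer's disease -related regions".

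**The concern.** Aim 5 is about moderation, so the second half of Hypothesis 5a most naturally says that the brain measures matter more in older adults. That is a statement about a difference in slopes, and the pooled model has no parameter for it.

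Two errors become possible. A significant age-group term could be taken as support for stronger moderation in older adults when the slopes are the same. A real difference in slopes could also go unreported because nothing in the model estimates it. Finding significance in one stratum and not in the other would not settle the matter, because that is not a test of the difference.

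**Working it through.** **Inputs from the documents.** The outcome, predictors and hypothesis are as quoted. Structural imaging is done only at baseline of phase 1, so each participant has one value per brain measure. The plan gives no sample size, power or test level for Aim 5, so there is no figure to reproduce.

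**Step 1: what the planned model estimates.** Let D be a participant's HS-to-SR difference in a Toolbox measure, and let older = 1 or 0.

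D = b0 + b1·cortical + b2·hippocampal + b3·WMH + b4·older + covariates + error

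- D is already the SR effect, so b1 to b3 are the moderation effects. The first half of Hypothesis 5a is testable.
- b1 to b3 carry no age index, so they are forced equal in the two age groups.
- b4 is the age difference in the SR effect at fixed brain measures.

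**Step 2: what the hypothesis needs.** Add c1·older·cortical + c2·older·hippocampal + c3·older·WMH. The older-adult slope for cortical thickness is then b1 + c1 and the younger-adult slope is b1, so the age difference in moderation is c1 (likewise c2 and c3). The planned model sets c1 = c2 = c3 = 0. This is algebra and rests on no assumed number.

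**Step 3: size, by simulation.** Assumptions: three standardised brain measures, the first of which affects D; residual SD 1; two-sided 5% tests; ordinary least squares. Group sizes are assumed: 10 older v 50 younger (50 is the expected number of completers in the parent cohort), and 8 v 28 (8 + 28 = 36, the completers reported under Subjects, split by assumption). The age shift is a shift in mean D.

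| Assumed truth | Test | 10 v 50 | 8 v 28 |
|---|---|---|---|
| Slopes 0.5 in both groups, age shift 1 SD | Planned age term | about 79% | about 62% |
| Slopes 0.8 older v 0 younger, no shift | Planned age term | about 9% | about 7% |
| Slopes 0.8 older v 0 younger, no shift | Added interaction, measures independent | about 47% | about 35% |
| Slopes 0.8 older v 0 younger, no shift | Added interaction, measures correlated 0.5 | about 33% | about 24% |

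In the first row moderation does not differ, and the added interaction test rejects at about its nominal 5%.

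**Step 4: rough hand check of precision.** With independent measures, SE(c1) ≈ √[1/(n_older − 4) + 1/(n_younger − 4)].

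- 10 v 50: √(1/6 + 1/46) = √0.188 = 0.43. With 60 − 8 = 52 degrees of freedom, the 95% half-width is about 2.01 × 0.43 = 0.87.
- 8 v 28: √(1/4 + 1/24) = √0.292 = 0.54. With 36 − 8 = 28 degrees of freedom, the half-width is about 2.05 × 0.54 = 1.11.

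Both half-widths exceed the assumed slope difference of 0.8, in line with the modest power above.

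**The case against.** **Wording.** The second sentence of Hypothesis 5a could refer to the SR effect on cognition itself, the grammatical subject of the sentence before it. The pooled age term would then address it, adjusted for brain structure. A reader might reply that this only repeats Hypothesis 4a. That goes too far: the Aim 4 unpaired t-test compares unadjusted means, and the two differ whenever brain structure differs by age. The ambiguity is therefore real. The moderation reading remains the more natural one in an aim about moderation, and the text should say which is meant.

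**Stratified models.** A reader might infer that the plan cannot answer the age question at all. The documents do not support that. Without covariates, the stratified slopes equal those of the fully interacted pooled model, so their difference can be recovered. What is missing is a planned contrast with its standard error.

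**Misreading.** A reader might also infer that the investigators would treat the age term as evidence of moderation, or would compare which stratum is significant. The plan says neither. These are risks of leaving the inference unspecified.

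**Numbers.** The group sizes are assumptions. Under Study Design, only parent-cohort participants enrolled during the supplement award receive the added cognitive and imaging assessments, so 50 or 28 younger adults with Aim 5 data may be too many. This bears on the illustration; the algebra in Steps 1 and 2 does not depend on it.

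**Conclusion.** The concern holds for the second half of Hypothesis 5a on its natural reading. The pooled model forces common moderation slopes, its age coefficient does not measure a difference in moderation, and no comparison of the stratified slopes is planned. The first half of the hypothesis can be tested as written.

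The structural conclusion needs no numerical assumption. The percentages are illustrations under assumed group sizes, slopes and correlations. They show that the age term can be significant in most trials when moderation is equal, and close to its nominal rate when moderation differs strongly. The reference to cortical *length* is a separate wording slip, since the hypothesis concerns thinning and the imaging section derives thickness.

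**What to change.** - State in Hypothesis 5a that the second sentence refers to the moderation.
- Add age group × cortical thickness, age group × hippocampal volume and age group × WMH volume to the pooled model.
- Base any conclusion that moderation is greater in older adults only on these slope differences, reported with confidence intervals.
- Replace *cortical length* in both Aim 5 models with the average thickness in Alzheimer's disease-related regions, as defined in the imaging section.
- Label the added terms as post hoc, because Renewal Information records the study as closed to enrolment and limited to data analysis.
- Do not require centring within age group. It leaves the interaction coefficients unchanged and, in the fully interacted model without covariates, turns the age term into the unadjusted group difference already tested in Aim 4.

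The cost is a wording change and three extra terms per outcome, with no new data. The drawback is imprecision: with few older adults the slope differences will have wide intervals, and a non-significant result should not be read as equal moderation.

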
effects on weight gain and adipose tissue mass increase. Hypothesis 1b. EE, assessed by DLW, and physical activity level, monitored daily by actigraphy, will be lower during SR relative to HS. We will perform repeated measure linear mixed model analyses separately for DLW and actigraphy-derived variables as the responses. Sleep duration (SR vs. HS) and the covariates will be used as independent variables. Subject will be used as a random effect. Paired t-test and Wilcoxon test will be used to determine whether SR and HS have different effects on DLW and actigraphy measures. Sp. Aim 2: Hypothesis 2a. EI, assessed by [3-d food records], will be greater during a period of SR relative to HS. This will be mostly due to increased fat and carbohydrate intakes. We will perform a repeated measure linear mixed model analyses separately with each EI measure (as the response) and sleep duration (SR vs. HS) and the covariates as independent variables. Subject will be used as a random effect. Paired t-test and Wilcoxon test will be used to determine whether the SR and HS have different effects on EI measures. Hypothesis 2b. Neural responses to food stimuli, assessed by fMRI after 6 wk of SR or HS, will indicate increased activity in networks associated with reward and food valuation (insula, orbitofrontal cortex) during a period of SR relative to HS. These responses will be correlated with intakes of high carbohydrate and high fat foods (hypothesis 1a) and [ghrelin]. Connectivity of the networks involved in reward valuation at rest will be stronger after SR compared to HS and synchrony of the DMN will be reduced after SR compared to HS. Sp. Aim 3: Hypothesis 3a. SR will lead to [increased glucose, insulin, triglycerides, and reduced highdensity lipoprotein cholesterol and adiponectin relative to HS.] We will perform repeated measure linear mixed model analyses separately for each of glucose, insulin, triglycerides, high-density lipoprotein cholesterol and adiponectin. Sleep duration (SR vs. HS) and the covariates will be used as independent variables. Subject will be used as a random effect. One-sided paired t-test and Wilcoxon test will also be used to determine whether the SR and HS have different effects on the cardio-metabolic risk profiles, as well as the direction of the effects. Hypothesis 3b. Increased adiposity and poor diet quality (higher fat and carbohydrates) after SR will partially explain the adverse cardio-metabolic risk profile associated with SR. We will select the cardiometabolic risk profile variables that are adversely associated with SR. Then, we will compute the difference in those variables in SR vs. HS (i.e. the value of each variable in SR minus the value of that variable in HS). Using a linear model analysis, we will test if these differences are associated with increased adiposity and poor diet quality. If, for some variables, there are multiple observed differences for each subject then a linear mixed model analysis will be used with subject as a grouping variable. A separate analysis will be performed for each such difference, with the difference as the response variables and adiposity, food quality variables and the covariates as dependent variables. *Linear Mixed Model Analyses.* We will fit a linear mixed model to analyze the data. Treatments (SR vs. HS) will be used as fixed effects and subject will be used a random effect. The other independent variables, such as demographic variables, will be covariates. Those covariates will be removed if they do not significantly contribute to the model. Aim 4: (To determine whether long-term mild SR, relative to HS, challenged acute cognitive outcomes in older and younger adults. Hypothesis 4a. Mild SR will induce cognitive decline, assessed using with the NIH Toolbox, which will be greater in older relative to younger adults.) Outcomes are measures from the NIH Toolbox. Each outcome will be analyzed in separate linear mixed model analyses, for older and young participants, as detailed in "*Linear Mixed Model Analyses*" section above. Sleep (SR vs. HS), along with phase (1 vs. 2), carryover effects, and covariates (if they are found to be significant in an initial analysis) will be used in the model. Subject will be used as a random effect. Then, we will pool the datasets to include both older and young participants. In the pooled dataset, we will use the average differences in NIH Toolbox measures (from HS to SR) as outcomes in linear model analysis. Age group (older vs. younger) will be used as main predictor variable. We will also apply covariates as independent variables, if they are found to be significant in an initial analysis. We will use unpaired t-test on the average difference in

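### The three Aim 6 mediation models omit phase, so a phase shift in both hormone and cognition can pass for mediation even with balanced sequences

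*Combined protocol and SAP*

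**What the plan says.** Under Statistical Procedures, Aim 6 uses a three-step Baron and Kenny analysis. It is run separately for older and younger participants, with subject as a random effect.

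- **Step 1**, cognitive score: "Within each mediation analysis, the first analysis will only have one fixed effect: sleep (SR vs. HS".
- **Step 2**, hormone: sleep is again the only fixed effect.
- **Step 3**, cognitive score: "Fixed effects will be sleep and the hormone measure".
- **Rule:** steps 1 and 2 must both be significant for sleep. Mediation is then concluded under the condition "If the hormone measure is still found to be significant, and the coefficient of sleep has decreased in absolute value from the first analysis".

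Two other places in the section bear on phase. For the same NIH Toolbox outcomes, the Aim 4 models use "Sleep (SR vs. HS), along with phase (1 vs. 2), carryover effects, and covariates". The Statistical plan paragraph says "we will test for carryover effects by using a treatment x phase interaction in an initial version of each linear model", followed by "If the interaction term is not significant then we will rebuild the linear model without the interaction term".

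Hypothesis 3b regresses SR minus habitual sleep (HS) differences on adiposity and diet quality: "with the difference as the response variables and adiposity, food quality variables and the covariates as dependent variables". It does not say whether those predictors are also differences. In Procedures, Image analysis, the group-level task-fMRI comparison of HS with SR is a paired t-test.

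**The concern.** A balanced crossover protects the sleep effect from a phase shift, so it is natural to assume that it protects the mediation analysis too. That holds for steps 1 and 2. It does not hold for step 3, where the hormone is an observed variable that carries its own phase shift. If the score also shifts, hormone and score move together across phases for a reason unrelated to mediation.

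Such shifts are plausible, though the documents do not measure them. The Toolbox is taken at baseline and week 6 of both phases, which is four times, so practice may raise later scores. The counterbalanced forms in Study Design are described for the ModRey. Phase 2 generally starts about 12 weeks after phase 1 (6-week phase plus 6-week washout), so hormone levels could drift. At stake is a mediation claim that reflects calendar order, or a real mediator that is missed.

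**Working it through.** **1. The plan's own figures.** None is given for Aim 6 or for phase effects. The only related figures are the paired-test powers. The effect sizes 0.69/0.36 = 1.92 and 0.91/0.65 = 1.40, with power above 99% at 50 completers, reproduce and are not affected by this point.

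**2. Why balance does not help.** Let s = +1 if SR falls in phase 2 and -1 if it falls in phase 1. Scale each within-person SR-HS difference to a residual SD of 1. Let d be the SR effect and p the phase shift:

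- hormone difference = dH + pH·s + error
- score difference = dY + pY·s + error

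With no true link, regressing one difference on the other without s gives

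slope = pH·pY·Var(s) / (pH²·Var(s) + 1)

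Under balance Var(s) = 1:

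- 0.25/0.25: 0.0625/1.0625 = 0.059
- 0.25/0.5: 0.125/1.0625 = 0.118
- 0.5/0.5: 0.25/1.25 = 0.20

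At a 70:30 split Var(s) = 1 - 0.4² = 0.84, and 0.5/0.5 gives 0.21/1.21 = 0.17. The spurious slope is therefore largest at exact balance. If only one variable shifts, it is zero.

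**3. Effect on the rule.** The step 3 sleep coefficient is about dY - slope × dH. With dY = dH = 0.8 and slope 0.20 it falls to 0.8 - 0.16 = 0.64, and the rule can fire. With slope -0.20 it rises to 0.96, and the rule rarely fires. Shifts are called aligned when the product of the two shifts has the same sign as the product of the two SR effects.

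**4. Sample size available.** Subjects reports 36 completers over both age groups. Aim 6 analyses the groups separately. Study Design gives the cognitive tests only to those parent-cohort participants who entered during the supplement award. So 36 is an upper bound for any one Aim 6 analysis. The value 24 is an illustration. The value 13 is 79 (target accrual) minus 66 (parent enrolment), an assumed size for the older group.

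**5. Simulation of the full rule.** Settings: random-intercept model fitted by REML, two rows per person, between-phase correlation 0.8, sequences as equal as n allows, no true link, shifts of 0.5 SD in both variables and aligned, two-sided 5% (the plan states no alpha). False mediation, without / with phase:

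| n | SR effects 0.8 SD | SR effects 0.4 SD |
|---|---|---|
| 36 | 14% / 2% | 5% / 1% |
| 24 | 9% / 2.5% | 2% / under 1% |
| 13 | 3% / 2% | 0.4% / 0.2% |

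For SR effects of 0.8 SD, repeat runs gave 14-15%, 9-11% and 3-4% without phase, and 2-3% with it. With shifts of 0.25 SD in both, the rate is no more than about 5%.

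**6. Opposed shifts.** At n=50, used only for illustration because Aim 6 cannot reach it, false mediation falls to 0.2%. Power for a true link of 0.4 drops from 96% to 69% when the total shifts are -0.5 and +0.5.

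**7. Hypothesis 3b, only if its predictors are SR-HS differences.** The step 2 formula applies directly. At n=36 with equal sequences, the slope is falsely significant in 6% (0.25/0.25), 9% (0.5/0.25) and 22% (0.5/0.5).

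**8. Task fMRI.** Under balance there is no bias, only lost precision. For a single test at n=36 and a 0.4 SD effect, power is 0.55 against 0.65 with phase if the phase effect is 0.5 SD.

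**The case against.** **No phase effect is documented.** This stands. Every shift above is an assumption. Aim 6 also speaks of changes in hormones and cognition, and each phase has a baseline. If change scores are analysed, a stable shift cancels and only unequal practice gain or unequal drift between phases remains. The model text does not say that change scores are used.

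**The significance steps block most of the error.** This largely stands for modest SR effects or small samples, as the table shows. It does not stand for large SR effects on both variables at n=24 to 36.

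**The general plan already covers phase.** The Statistical plan sentence about each linear model could be read as reaching Aim 6. But Aim 6 says that step 1 has only one fixed effect, and the general sentence does not say that a phase main effect stays once the interaction is dropped. The passages conflict, and the general one does not supply the missing term.

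**Stronger readings.** A reader might take the 50 planned completers as the Aim 6 sample and arrive at about 17% false mediation. The separate age-group analyses, the partial testing of the parent cohort and the 36 completers rule that out. A reader might also infer that the paired t and Wilcoxon tests of Aims 1-3 are invalid. With balanced sequences they are unbiased and slightly conservative, and averaged over simple random allocation their error is about 5%.

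**Conclusion.** The point holds for Aim 6. All three models omit a design factor that Aim 4 includes for the same scores, and balance does not protect the hormone term in step 3. The size is moderate and conditional. It needs shifts near 0.5 SD in both variables, aligned with sizeable SR effects on both, and an analysis of levels rather than change from each phase's baseline. Under those conditions false mediation is roughly 9-14% instead of 2-2.5% at n=24 to 36. Outside them the inflation is small, and opposed shifts mainly hide true mediation.

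The documents do not support extending this to a claim that phase is ignored throughout. The sleep effects in Aim 6 steps 1 and 2 are unbiased under balance. The Aim 4 mixed models name phase, and the Aim 1-3 mixed models can be read as keeping it. The paired tests, the Aim 4-5 difference models and the carryover pre-test raise questions of precision, wording or preference, and are not part of this finding.

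**What to change.** - Add phase as a fixed effect in all three Aim 6 models. Reconcile the Aim 6 text with the Statistical plan paragraph and with Aim 4. State whether levels or changes from each phase's baseline are analysed.
- State whether the Hypothesis 3b predictors are SR-HS differences. If they are, add sequence to that model.
- For precision only, add sequence (which carries the phase effect in a within-person difference) to the group-level task-fMRI comparison, which has no other HS-versus-SR group test.
- Renewal Information reports published lipid and inflammatory results and a cognitive paper in press. Label any re-analysis of these as a sensitivity analysis.

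The cost is one degree of freedom per model, which matters slightly in the small older group. Phase is known from the design, so no new data are needed. Adjusting for phase removes this confounder of the hormone-cognition path and no other.
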